Along with decrease beta-cell function, youth with type 2 diabetes become resistance to pharmacological mono-therapy (metformin or rosiglitazone) and lifestyle intervention such as change in diet and physical activity. Due to these limiting factors, once a pre-diabetic child or adolescent develops type 2 diabetes, it is considered irreversible (Zeitler et al, 2012.) Given this, the focus is on early prevention of on-set prediabetes or type 2 diabetes among the obese youth population. Early lifestyle prevention and intervention programs consist of changing diet, physical activity and lifestyle habits (i.e taking the stairs instead of the elevator) through education. A number research study-programs have shown promising results in regards to diabetes prevention such as: 42% reduction of whole body insulin sensitivity, a two- fold greater change in body fat than body weight, increase lean body mass, and normalized fasting, two-hour plasma blood glucose levels, and decrease LDL cholesterol levels (Shaw, 2009, Wadden, 2012.) In addition to the physical and metabolic impact of obesity, research supports the relationship between obesity, mental health, and health behaviors. Generally, overweight and obese youth have increased mental health concerns compared to their normal weight peers (Sinha, 2002.) Specifically, obesity has been linked to presence of depression, anxiety, attention deficit hyperactivity disorder, and conduct disorder among children (Halfon, 2013, Puder, 2010.) Difficulty coping with stress and decreased selfesteem are also associated with obesity (BeLue, 2009.) Studies have also shown that individuals, adults and youth, with type 2 diabetes have decreased cognitive functioning including mental processing speed, flexibility, memory, and learning (Puder, 2010.) Physical activity participation has been linked with improved academic performance, mental health, and cognitive function (Hillman, 2008.) Despite these findings, the best treatment or weight management for childhood obesity is still uncertain. A few studies have examined the cumulative impact of improving physical activity, fitness, nutrition, and overall health behaviors in children.

The specific aims of this research project are to:

- 1) Examine the change of health status of youth participants over time as a result of the 12-month (16 weekly, 3 biweekly, and 6-monthly session) ISC intervention through the evaluation of metabolic, physical fitness, and health habit parameters

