On the day of registration, parents or guardians will receive project information packets from the trained research team. The packets will include a parent/guardian consent form, a child assent form, and detailed participation requirements, benefits, and incentives. Once the researcher consents the parent and assents the child face-to-face, the child and parent will be asked to sit with the researcher to complete the study questionnaires. The parent will complete the Healthy Habits Questionnaire (parent version), the child and parent will complete the Healthy Habits Questionnaire (child version), and the child (child version) and parent (parent version) will complete the mental health questionnaire separately. Trained research team members will complete all face-to-face consenting and surveys/questionnaires. Upon consenting the family (parent and child/children) will be assigned, to either the ISC. Once completed the participant will return the following week to complete their pre-evaluation assessment.

The parents will be encouraged to contact the research team if they should have any questions regarding the study procedures. All questionnaires, consents, and assent forms must be completed prior to the data collection days with the assistance of a research team member. The research staff will review all materials and assign a study id prior to the child's participation in data collection. Following completion of the project parents or guardians of all children enrolled in the project will receive a report of their health behaviors, physical fitness, and mental health performance with strategies to improve/maintain their outcomes. The research team member will also inform the parent and child that video recording and pictures of the educational sessions, physical activity sessions, and evaluation sessions (only physical fitness measures) will be taken by a research team member for the use of dissemination and presentations regarding the findings. If parents do not wish to consent and child does not wish to assent to video recordings or photography of this nature the research team will make a note and respect the participants' wishes.

4. Research Design,

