
strength with the elbow bent at a 90-degree angle (National Institute of Health, 2012.) Components of the Bruininks-Oseretsky Test of Motor Proficiency, Second Edition (BOT-2), an array of goal-directed activities, will be used to measure fine and gross motor control skills, balance, abdominal, and upper body strength (Bruinimks, 2005). The wall squat test was used to assess lower body strength and endurance, specifically for the quadriceps muscle group (Welk, 2008). The vertical jump test data were used to estimate average power (watts) according to the Lewis formula (Fox, 1974): Average Power (Watts) = $\sqrt{4}$. 9 x mass (kg) x \sqrt{VJ} (m) x 9.81. A sit-and-reach box (Flexer-tester, Novel Product Inc., USA) was used to assess lower back and hamstrings flexibility.

ISC Educational and Physical Activity Sessions:

- Education Curriculum Overview: The lesson portion will include health education session (e.g. nutrition, exercise, etc.) and session activity. This will take about 45 minutes to complete in each session.
- Physical Activity Curriculum Overview: All physical activities will include low to moderate intensity (body weight only) exercises such as: push-ups, dancing, jumping jacks, curl-ups, squats, skipping, stretching, brisk walking, and jogging/marching in place. Sports and games will also be offered such as: basketball, badminton, volleyball, tag, jump rope, and scavenger hunts. The is will take about 45 minutes to complete in each session.

Intervention Session and Evaluation Timeline and Dates:

Visit 1: Consent, register participants, questionnaire completion

• The first visit will be for program registration and consenting at the Gaisman Community Center. Research staff will consent parents, assent children, and sit face-to-face with the parent and child to complete the Healthy Habits and mental health questionnaire. This will take about 1-2 hours to complete.

Visit 2: Pre-Evaluation

- All physical activity, physical fitness, and health measures described will be collected at the
 Gaisman Community Center. This will take about 1-2 hours to complete. The drop-off/pick-up
 home visit appointments will also be scheduled in order to collect physical activity data described
 in the health behaviors measures. The child will be asked to wear the activity monitor for 7-days
 hours. The drop-off home will take 30 minutes. The pick-up home visit will take 30 minutes. Both
 home visits will add up to 60 minutes to complete.

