47.1 * Will any drug/biologic, device or intervention being administered and evaluated as a diagnostic, monitoring or to procedure in this study/project be provided free of charge?	eatment
47.0 (3100) Financial Obligations	
The payment (YMCA membership) will be prorated based on the completion on evaluation session. At consenting/registration the parent/child will be given a 3 month YMCA family membership. At the completion of the intervention portion or the program and post evaluation the parent/child will be given an additional 3 month YMCA family membership. Therefore 2 payment amounts will be given.	
* If your answer is the second option, "Prorated payments forprocedures," please describe the schedule of payments for specific visits and/or procedures. * If your answer is the third option, "Prorated payments plus a bonus for completing the entire study," describe the schedule of payment for specific visits and/or procedures, as well as the bonus for completing the entire study/project.	
completed, plus a bonus will be paid for completing the entire study/project Not applicable; no money will be paid to the subjects	
completed Prorated payments will be processed or issued at the time specific visits and/or procedures are	
 Lump sum payment will be made at completion of the study/project (Note: if paying per visit, the payment must not be held until the end of the study because of potential undue inducement; the same applies if a rather large sum of money will be paid only at the end of the study.) Prorated payments will be processed or issued at the time specific visits and/or procedures are 	
46.3 * How will the actual amount of money received by the subjects or their legally authorized representative be deter	mined?
Child: incentive of their choice (ex. food log, water bottle, jump rope, exercise band, label reading guides, pedometer, etc.) Parent/Child: YMCA memberships, \$50 gift cards (from Kroger or Walmart) for the family each data collection section	
* Please explain:	
The subject's legally authorized representativeMixed arrangement, depending on the age or health of subjects	

48.1 * Does the research include procedures that have the potential to cause physical injury to the subjects?

O No. The research DOES NOT include procedures that have the potential to cause physical injury to the subjects.
49.0 (3210) Potential Injury
49.1 * Who will be responsible for the costs of treating research-related physical injuries?

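### The first YMCA membership is issued about a week before baseline activity is measured, and later change mixes programme effect with membership access

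*Combined protocol and SAP*

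**What the plan says.** **Payment (Section 46.3).** The memberships are a participant payment: "The payment (YMCA membership) will be prorated based on the completion on evaluation session". The first comes at the start: "At consenting/registration the parent/child will be given a 3 month YMCA family membership". The second comes later: "At the completion of the intervention portion or the program and post evaluation the parent/child will be given an additional 3 month YMCA family membership". The section closes with "Therefore 2 payment amounts will be given". The Incentives paragraph in Section 21.1 item 4 lists gift cards and a raffle but no membership.

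**Baseline (Section 21.1 items 3 and 5).** At the consent visit, "the child and parent will be asked to sit with the researcher to complete the study questionnaires". Then: "Once completed the participant will return the following week to complete their pre-evaluation assessment". The fitness and metabolic measures are taken at that pre-evaluation (Visit 2). The monitor home visits are also scheduled there: "The child will be asked to wear the activity monitor for 7-days".

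**Evaluations.** Section 21.1 item 4 gives Weeks 1, 8 and 16 and months 6, 9 and 12, in a single-group design whose whole 12 months are called the intervention phase. The Section 30.1 table puts the post-evaluation at 3 months. Section 34.2 places the maintenance assessments 3, 6, 9 and 12 months out.

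**Aims and model.** Aim 1 is to "Examine the change of health status of youth participants over time as a result of the 12-month" ISC intervention, and Aim 2 is worded the same way for parents and the adult sessions. Neither analysis statement (Section 21.1 item 6, Section 34.3) has a term for membership status or use.

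**The concern.** A family YMCA membership plausibly makes physical activity easier. That is an inference about what a membership offers, not something the documents state. If it is in hand before baseline activity is recorded, the baseline is not a pure pre-programme value. Accelerometer activity is the first measure listed in both outcome sections, and it is the one that could respond soonest.

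The second issue is attribution. Every family receives the memberships, there is no comparison group, and the model does not carry membership. Change over time then reflects the ISC sessions and the availability of the facility together. A fall at a late evaluation, which Section 34.2 would read under maintenance, could be a fading programme effect, the loss of free access, or both.

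**Working it through.** The plan gives no figure on this point to reproduce, so the check is calendar arithmetic.

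**Inputs**
- Consent = Week 0; pre-evaluation = Week 1 (Section 21.1 item 3).
- Each membership lasts 3 months: 3 × 365.25 / 12 / 7 = 13.04 weeks (Section 46.3).
- Months 6, 9 and 12 = Weeks 26.1, 39.1 and 52.2.
- Assumption: each membership starts on the day it is issued. No activation date is given.

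**Baseline.** The first membership is issued at Week 0. The questionnaires are completed at the same visit, so they precede any use. Fitness and metabolic measures are taken at Week 1, after about one week of possible access. The 7-day wear starts after Visit 2, so it ends at Week 1 + 1 = Week 2 at the earliest.

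**Access on the Section 21.1 item 4 schedule.** Membership 1 runs from 0 to 0 + 13.04 = Week 13.0. Membership 2 runs from 16 to 16 + 13.04 = Week 29.0.

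| Evaluation | Week | Access | Distance from lapse |
|---|---|---|---|
| Pre | 1 | on | 12.0 weeks before |
| Mid | 8 | on | 5.0 weeks before |
| Post | 16 | off | 16 − 13.04 = 3.0 weeks after |
| Month 6 | 26.1 | on | 29.04 − 26.09 = 3.0 weeks before |
| Month 9 | 39.1 | off | 39.13 − 29.04 = 10.1 weeks after |
| Month 12 | 52.2 | off | 52.18 − 29.04 = 23.1 weeks after |

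**Other timings in the documents**
- *Visit list at one visit per week up to Visit 20, later months counted from the pre-evaluation:* the post-evaluation falls at Week 19, which is 6.0 weeks after the first lapse. Membership 2 runs to Week 32.0, so access is on at month 6 and off at months 9 and 12 (8.1 and 21.1 weeks after lapse).
- *Section 30.1, 3-month post-evaluation, with months 6, 9 and 12 taken from Section 21.1:* counted from consent, the first lapse falls on the day of the post-evaluation; counted from the pre-evaluation, it comes 1.0 week before. The second lapse falls at month 6, and months 9 and 12 are off.
- *Section 34.2, post-evaluation at Week 16:* membership 2 ends at 3 months out, and access is off at 6, 9 and 12 months out.
- *Intervention portion in Section 46.3 read as the full 12-month phase:* membership 2 starts at Week 52.2 and covers no evaluation. Access is off at Week 16 and at months 6, 9 and 12.

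Access changes between evaluations in every reading. At most 3 + 3 = 6 of the 12 months (50%) are covered.

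**The case against.** **The lapse dates are not fixed by the documents.** This stands. A reader might infer that both memberships definitely run out before the key evaluations. The documents do not support that. Month 6 is covered on the Section 21.1 item 4 schedule, the first lapse can coincide with the post-evaluation, and the second membership may not begin until after the last evaluation. Only the statement that access changes between evaluations holds throughout.

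**Baseline contamination is narrow.** This also stands. A reader might infer that the whole baseline is compromised, or that the programme effect is inflated. The questionnaires, including self-reported activity, are completed at consent. One week of possible access can hardly move A1C or lipids. If it raised accelerometer activity, the measured change from baseline would tend to shrink, which is conservative for a benefit claim.

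**The missing control group is the deeper cause.** True: any concurrent influence is mixed into change over time in this design. A control group given the same memberships would remove this one from a between-group comparison. Section 21.1 item 4 has no control group, although Section 21.1 item 3 and the third aim in Section 22.1 still refer to one. The membership remains worth naming, because it is supplied by the study itself and its first issue can be re-timed.

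**Months 9 and 12 are not off-programme.** Correct. Monthly sessions, each with 45 minutes of physical activity, continue up to the final evaluation. Any wording about those time points has to say so.

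**Some families may already be members.** Recruitment flyers go to all YMCA sites, so this is possible. The documents do not say, and it would only reduce the effect.

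**Conclusion.** The point holds as a minor improvement. Issue at consent and the one-week gap to the pre-evaluation are explicit, so baseline accelerometry, and less plausibly the fitness and metabolic measures, follow the start of an activity-related incentive. The likely direction is a smaller change from baseline.

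With one group and no membership term, later change cannot separate programme effect from membership access. The on, on, off, on, off, off pattern rests on the Section 21.1 item 4 schedule and on membership starting at issue. The effect in outcome units cannot be calculated, because activation dates and use are not given. Nothing here makes the study's results invalid; it limits what the conclusions can attribute to ISC alone.

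**What to change.** 1. Issue the first membership only after the pre-evaluation and the 7-day baseline wear are complete. The incentive then comes one to two weeks later (one week to the pre-evaluation plus 7 days of wear), or slightly more if the monitor drop-off is not prompt. This protects the baseline only. Issued at Week 2, the membership would end at 2 + 13.04 = Week 15.0, still before a Week 16 post-evaluation.
2. State in the aims and conclusions that the package evaluated is ISC plus YMCA membership. This changes wording only.
3. On the Section 21.1 item 4 schedule, describe months 9 and 12 as after the weekly and biweekly sessions and the membership have ended, with monthly sessions continuing. This also changes wording only.
4. Reconcile the evaluation and payment timing in Section 21.1 item 4, the Section 30.1 table, Section 34.2 and Section 46.3, and say which point in the programme triggers the second membership.

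Recording when each membership is activated and whether it is used would be a useful small addition, since steps 1 to 4 do not stop access from changing between evaluations.

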61.0 Save and Attach Documents

61.1

The following text box is provided in the event that you need to share additional information with the Review Board.

[name] is a UT graduate assistant.

61.2 After clicking the "Save and Continue" button, you will advance to the routing form in order to attach any supporting documents (such as consent forms) and to send the submission to the necessary personnel for their signatures.

CLICK on "Save and continue..."
